therapeutics such as discussed above, the addition of immunomodulators to the treatment regimen appear to be an excellent choice for agents which can reduce the pathogenicity of this disease by reducing the dysregulation of autoimmunity which is destructive of normal tissue and when unchecked rapidly leads to mortality. The use of naltrexone will be done in a randomized, double blinded manner whereas the use of ketamine will be unblinded and given as a rescue agent should a patient progress. Additionally should a patient be ineligible for the randomized portion of the study due to already being in stage 2B or stage 3 of the disease, they will be given the opportunity to enter the trial to receive ketamine without being randomized to naltrexone vs placebo.

3. Approach

Specific Aims

Aim 1: Determine whether treatment with low dose naltrexone, 4.5 mg by mouth daily, reduces progression of patients with COVID-19 from stage 1 or stage 2A to stage 2B or stage 3.

- 1.1: Determine the percentage of patients on naltrexone who proceed to requiring advanced oxygenation (hiflo nasal canula, non-rebreather, CPAP, BIPAP, or intubation)**
- 1.2: Determine the impact of naltrexone on development of renal failure, liver failure, cytokine storm, and ARDS.**
- 1.3: Determine the impact of naltrexone on mortality, length of stay, admission to ICU, length of stay in ICU, intubation, length of intubation, and time till recovery.**

Aim 2: Determine if ketamine can improve mortality in patients who progress the need for advanced oxygenation.

- 2.1: Determine the impact of ketamine on development of renal failure, liver failure, cytokine storm, and ARDS.**
- 2.2: Determine the impact of ketamine on mortality, length of stay, admission to ICU, length of stay in ICU, intubation, length of intubation, and time till recovery.**

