Patients who consent will be randomized to one of 2 arms: Arm 1 – low dose naltrexone 4.5 mg by mouth per day (can be given via NG tube if needed). Arm 2 – placebo by mouth per day. Treatment will be for 30 days past discharge. If the patient develops severe insomnia or shows symptoms of opioid withdrawal the dose of naltrexone can be decreased to 3 mg by mouth per day. If the patient continues to demonstrate issues on the 3 mg reduced dose of naltrexone the dose can be further reduced to 1.5 mg by mouth per day or held temporarily if needed. Reasons it may need to be held include if it is interfering with sedation, due to the unique issues with sedation in COVID-19 often requiring large amounts of opioids. Even low dose naltrexone seems to interfere with sedation in some of the patients. Since opioids, particularly fentanyl, are stored in fat, a patient who is starting on study who has been on opioid based sedation for 3 days or more can be started on a reduced dose of naltrexone (as above) or the naltrexone can be held from start and only ketamine used until their sedation is weaned to levels where clinically it is felt the naltrexone will no longer cause issues with sedation or signs of withdrawal. A patient should have naltrexone started by the time ketamine is no longer needed.

Imaging data, flowsheets, and medical notes will be abstracted to generate a daily summary of the patient's status to determine renal failure, liver failure, cytokine storm, ARDS, improvement vs progression of disease, need for advanced oxygenation, ICU status, and mortality.

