If at any point a patient requires advanced oxygenation (hiflo nasal cannula, non-rebreather, CPAP, BIPAP, or intubation) for more than 15 minutes they will then be given ketamine as a rescue treatment and remain on the Naltrexone or placebo. Ketamine will initially be given at a dose of 0.15 mg/kg based on total body weight (max 20 mg) every 6 hours (+/- 1 hour) by intravenous piggyback over 30 minutes. Ketamine will continue until the patient is deemed stable for low level oxygen. If the patient relapses after the ketamine is stopped they can be restarted on the ketamine. If the patient continues to worsen or displays evidence of cytokine storm (elevated markers of inflammation, evidence of ARDS, continuous fever) the dose of ketamine will be increased to 0.3 mg/kg IV every 6 hours (max 30 mg). The dose of ketamine can be reduced back to 0.15 mg/kg at the clinical decision of the physician investigators. If a patient has issues with hypertensive emergency the dose of ketamine can be held until the hypertensive emergency is controlled.

In addition, a patient can receive ketamine if they are not yet on advanced oxygenation if the investigating physician feels they are moving toward cytokine storm based on the markers of inflammation and clinical factors such as worsening imaging and unrelenting fever. If a patient transitions to comfort care the patient will remain in the study for data collection purposes. Study medications may be held if requested by the clinical team, patient, LAR or family.

Patients who at screening are already requiring advanced oxygen can be consented and enrolled in the study and immediately will skip the randomization and be placed on naltrexone and receive ketamine as the starting treatment in an open label manner.

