3.2 Measurements of Outcomes

Primary Outcome Measure:

1. Progression of oxygenation needs

Count of participants initially presenting with mild/moderate disease who progress to requiring advanced oxygenation (high flow nasal canula, non-rebreather, continuous positive airway pressure (CPAP), bilevel positive airway pressure (BIPAP), or intubation)

[Time Frame: up to 1 month]

Secondary Outcome Measure:

2. Renal failure

Count of participants who develop or experience worsened renal failure as defined by RIFLE criteria, a 5-point scale where the categories are labeled: Risk-Injury-Failure-Loss-End stage renal disease, with Risk being the least severe and End stage renal disease being the most severe. The criteria for determination of stage are factors of serum creatinine and urine output. Numbers of participants worsening one or more RIFLE stages will be reported.

[Time Frame: up to 1 month]

3. Liver failure

Count of participants who develop or experience worsened liver failure as defined by serum transaminases five times normal limits

[Time Frame: Daily times 5, then weekly]

4. Cytokine Storm

Count of participants who develop cytokine storm as measured by elevated markers of inflammation (elevated D-dimer, hypofibrinogenemia, hyperferritinemia), evidence of acute respiratory distress syndrome (ARDS) measured by imaging findings and mechanical ventilator requirements, and/or continuous fever (≥ 38.1 ° Celsius unremitting)

[Time Frame: 1 month]

5. Mortality

Count of participants who die from COVID-19

[Time Frame: up to 1 month post hospital discharge]

6. Length of hospital stay

Length of hospital stay in days

[Time Frame: 1 month]

7. Intensive Care Unit (ICU) admission

Count of patients admitted to the ICU at any time during index hospitalization

[Time Frame: 1 month]

8. Intensive Care Unit (ICU) duration

Length of ICU stay in days

[Time Frame: 1 month]

9. Intubation

Count of participants requiring intubation

[Time Frame: 1 month]

10. Intubation duration

Length of intubation, measured in days

[Time Frame: 1 month]

11. Time until recovery

Time measured in days from hospital admission to determination patient is stable for discharge

[Time Frame: 1 month post hospital discharge.]

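### The ICU, intubation and stay outcomes under Aim 2.2 have no time zero at ketamine start, so ketamine figures can include events and days that precede the drug

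*Combined protocol and SAP*

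**What the plan says.** Aim 2.2 (section 3, Specific Aims) is to "Determine the impact of ketamine on mortality, length of stay, admission to ICU, length of stay in ICU, intubation", and it adds length of intubation and time to recovery.

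Section 3.2, Measurements of Outcomes, defines each outcome once, for both aims:

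- Item 7, ICU admission: "Count of patients admitted to the ICU at any time during index hospitalization".
- Item 8, ICU duration: "Length of ICU stay in days".
- Item 9, intubation: "Count of participants requiring intubation".
- Item 10, intubation duration: "Length of intubation, measured in days".
- Item 6 is hospital stay in days. Item 11 measures recovery time from hospital admission.
- Item 4, cytokine storm, begins: "Count of participants who develop cytokine storm as measured by elevated markers of inflammation".

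Section 3.1, Research Design, says when ketamine begins. Randomised patients receive it after more than 15 minutes of advanced oxygenation, a category that includes intubation. It also provides that "Patients who at screening are already requiring advanced oxygen can be consented and enrolled in the study"; these patients bypass randomisation and start on open-label ketamine with naltrexone. The same section makes provision for "a patient who is starting on study who has been on opioid based sedation for 3 days or more". The investigator may also start ketamine before advanced oxygenation is needed.

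The Statistical Analysis section promises descriptive statistics for all secondary outcomes. It estimates the non-mortality secondary outcomes as naltrexone-placebo differences. It also adds a chart comparison with matched patients from outside the study, for which it states no index date.

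**The concern.** An effect of ketamine on an event can be read only from what happens after the first dose, among patients who have not yet had that event. Here an outcome (intubation) is also a trigger for the drug, and some patients enter the study already on advanced support. Take a patient who is intubated in the ICU and then enrolled open-label. Under items 7 and 9 as worded, that patient can be scored as an ICU admission and as an intubation before receiving any ketamine, and the days already spent there can go into items 8 and 10.

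Ketamine figures built this way would partly describe how ill patients were at entry. The Statistical Analysis section says the secondary estimates will be used to plan future studies, and section 4 foresees a multi-centre trial. Event rates and durations that mix the periods before and after ketamine would be poor planning values for the ketamine part of such a trial.

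**Working it through.** **Plan's own figure.** The plan gives no figure on this point. Its one calculated design figure, 154 per arm, belongs to the primary outcome and is not affected.

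**Step 1. Set each definition against the start of ketamine.**

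| Item | Start of the count as written | Time before ketamine |
|---|---|---|
| 6 Hospital stay | none stated; frame 1 month | can be included |
| 7 ICU admission | any time in the index hospitalisation | included if it occurred |
| 8 ICU days | none stated; frame 1 month | can be included |
| 9 Intubation | none stated; frame 1 month | can be included |
| 10 Intubation days | none stated; frame 1 month | can be included |
| 11 Time to recovery | hospital admission | included |

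Only items 7 and 11 fix a window that reaches back before ketamine. For the other four the origin is undefined. Nowhere do the documents make the first ketamine dose the time zero for an outcome, exclude events already present, or start the day counts at that dose. The one procedure timed from ketamine start is the five-day laboratory series in section 3.1, which is not an outcome window.

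**Step 2. Can the event come first?** Yes, by two routes in section 3.1. A randomised patient may be intubated and then receive ketamine because of it. An open-label patient may already be intubated or in the ICU at screening. It need not come first, since ketamine can also follow a lesser form of oxygen support or precede advanced oxygenation. Hence *can include*, not *includes*.

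**Step 3. Illustrative size for the intubation count.** The documents do not give the share already intubated at the first dose, so these inputs are assumed:

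- p = share already intubated at the first dose: 20% to 60%.
- r = share of the remainder intubated later: 30%.

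Reported rate = p + (1 − p) × r

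- p = 20%: 0.20 + 0.80 × 0.30 = 0.44, or 44%.
- p = 60%: 0.60 + 0.40 × 0.30 = 0.72, or 72%.

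The later rate is 30% in both cases by assumption. The 28-point gap (72 − 44) comes entirely from status at entry.

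**Step 4. Illustrative dilution in a comparison.** Suppose ketamine truly cuts later events or days by 30%. Suppose also that a share g of the counted total, measured without that effect, precedes ketamine and is alike in both groups. The apparent reduction is 30% × (1 − g):

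- g = 10%: 30% × 0.90 = 27%.
- g = 25%: 30% × 0.75 = 22.5%.
- g = 50%: 30% × 0.50 = 15%.

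The documents give no value for g either. Steps 3 and 4 show the mechanism and its possible scale; they do not predict results.

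**The case against.** The strongest reply is that the plan specifies no ketamine contrast for these outcomes. The non-mortality secondary outcomes are to be estimated between the naltrexone and placebo arms, and the full analysis set holds only randomised patients. In that contrast, events after randomisation but before ketamine are legitimate. This stands, and it is why the randomised definitions should not be touched. It does not dispose of the point. Aim 2.2 is still stated, these are the only definitions available for it, and the descriptive statistics and the matched chart comparison are where ketamine-treated patients would be reported.

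Several stronger readings are tempting, and the documents do not support them:

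- *All these outcomes are counted over the whole hospital stay.* For ICU admission the text says so, and recovery time starts at admission. The others carry a one-month frame with no origin.
- *Cytokine storm and ARDS are miscounted in the same way.* Item 4 counts patients who *develop* cytokine storm, which reads naturally as new onset. ARDS is not a numbered outcome; in the outcome list it appears only as a component of cytokine storm.
- *Ventilator and ICU days are inflated by at least three days.* The three days in section 3.1 are days of opioid-based sedation. The text does not equate them with ventilator or ICU days, and it describes a contingency, not an expected share of patients.

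A further objection concerns the remedy. If days were re-anchored only for ketamine patients, comparators would still be counted from intubation or ICU entry, and ketamine would look better than it is. That is correct, and the fix has to cover both groups.

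**Conclusion.** The point holds in a limited form. The ICU, intubation and stay outcomes under Aim 2.2 are not anchored to the start of ketamine, and ketamine can start after some of those events. Ketamine figures built on the definitions as written can therefore contain events and days that the drug could not have influenced. The amount cannot be derived from the documents; the 44% to 72% range rests wholly on assumed shares.

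The primary outcome, the naltrexone-placebo estimates and mortality are not affected. A reader might infer that the missing time zero is the reason Aim 2.2 cannot be answered, or that repairing it would be enough. Neither follows. The plan has no specified concurrent control for ketamine, and open-label patients also receive naltrexone. Clean counting removes pre-treatment events but does not create a controlled comparison.

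**What to change.** Add a rule to section 3.2, Measurements of Outcomes, that applies to ketamine-treated patients only:

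1. Count ICU admission and intubation when they first occur after the first ketamine dose, among patients free of that event at that time.
2. State that *develop* in item 4 means new onset after that dose.
3. Count ICU, ventilator and hospital days, and time to recovery, from the first dose.
4. Report separately how many patients already had each event at the first dose.

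In the Statistical Analysis section, give each matched comparator an equivalent index date, defined by the same level of oxygen support and the same time since reaching it. Apply rules 1 to 4 to both groups from their respective index dates. Leave the definitions for the randomised naltrexone-placebo comparison unchanged.

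The cost is modest. The daily status summary in section 3.1 already covers oxygenation, ICU status, ARDS and cytokine storm, and oxygen delivery method and concomitant medications are recorded daily. Two drawbacks remain. At-risk denominators become smaller. And because ketamine can follow intubation on the same day, daily records will not always give the order of events, so it must be taken from chart times.

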3.1 Research Design

To date we have over 100 patients admitted to Beaumont, Royal Oak in the space of 1 week with about 25% needing to be admitted to the ICU. Of the first 101 patients admitted 25 ended up admitted to the ICU, 12 to the advanced COVID Unit (medical progressive care), and 64 to COVID general floor, these numbers can fluctuate and those in the COVID units can still progress to the floors. Approximately 70 of the 101 patients were treated with hydroxychloroquine and azithromycin.

This is a prospective, single center, randomized, double blinded study of naltrexone for the treatment of COVID-19 with an open label extension using ketamine as a rescue drug for patients who progress in their disease. We plan to recruit up to 500 patients. All COVID positive patients will be screened by the following criteria:

Inclusion	Exclusion
Positive for COVID -19	Known allergy to naltrexone
Admitted to Royal Oak	Known allergy to ketamine
Age \geq 18	Diagnosis of schizophrenia or acute psychosis
On \leq 6L Oxygen by nasal cannula ^A	Pregnancy
	On chronic high dose opioids > 90mg morphine mg equivalence
	Use of naltrexone or Vivitrol within 90 days

A – If on more than 6L oxygen by NC patient can be enrolled as a non-randomized patient directly into the ketamine rescue group.

If eligible the patient or their LAR will be approached for inclusion in the study. Given the nature of the pandemic and the shortage of personal protective equipment all consenting will take place over the phone in the presence of a witness as per IRB emergency safety policy during COVID19.

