Sample Size Determination: We assumed that 20% of patients admitted to the hospital will show progression to requiring more oxygen, and that we want to detect if naltrexone reduces the progression rate to no more than 10%. With these assumptions, a sample size of 154 per arm (308 total) is required to have 80% power based on a two-sample t-test, using PASS 16.

Secondary Outcomes: To examine the potential impact of ketamine on mortality, we will use the chi-squared test to evaluate the hypothesis that mortality is reduced in the naltrexone arm. We will also estimate the difference in proportions using the Bayesian approach noted above. We will use a type 1 error rate of 0.05 for this secondary outcome.

For all remaining secondary outcomes, we will estimate the difference between the two arms and not test for differences between the two arms since these data will be used in planning future studies. For dichotomous outcomes (renal failure, liver failure, cytokine storm, and ARDS), we will use the Bayesian approach discussed for estimating the difference in proportions. We will use generalized linear models to estimate the difference in durations (number of days in ICU, number of days on a ventilator, and length of stay), evaluating the distribution to use based on the data. We will consider using the Poisson, negative-binomial, and normal distributions. We will use a Bayesian approach, using a flat prior on the difference in means parameter. We will calculate 99% credibility intervals for all of these secondary outcomes given the multiple outcomes being examined.

For statistical analysis the biostatisticians and Data analytics teams at Beaumont ([name] and [name]) will pull patients who were not on SINK, had COVID-19 with as close to a direct match to patients with similar profiles who were treated on the SINK study. The match to the patients on SINK will aim to compare the outcomes of the two groups, to see if there is a difference in the outcomes. The evaluation is a chart analysis aimed at focusing on the outcomes of the study.

Safety Measures:

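### Time until recovery starts at hospital admission, so the two-arm comparison includes days before randomisation that the study drug cannot affect

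*Combined protocol and SAP*

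**What the plan says.** Section 3.2 Measurements of Outcomes, item 11, measures time until recovery as "Time measured in days from hospital admission to determination patient is stable for discharge". Item 6 is "Length of hospital stay in days"; it states no starting point, and the ordinary reading is admission.

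Under section 3.1 Research Design, a patient must already be an inpatient to be eligible ("Admitted to Royal Oak"). Consent is then taken by telephone before a witness, from the patient or a representative, and "Patients who consent will be randomized to one of 2 arms". No maximum interval from admission to randomisation is given. Nothing requires COVID-19 to be the reason for admission.

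Section 3.2 Statistical Analysis says that, for secondary outcomes other than mortality, "we will estimate the difference between the two arms and not test for differences between the two arms", because the results are meant for planning later studies. It also says: "We will calculate 99% credibility intervals for all of these secondary outcomes". Generalised linear models are assigned to ICU days, ventilator days and length of stay, with Poisson, negative-binomial and normal distributions as candidates. Time until recovery is not named there. No covariate for the lag between admission and randomisation is mentioned for any duration.

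**The concern.** A randomised comparison of durations normally starts the clock at randomisation, because only the time after it can differ between arms through treatment. Starting at admission adds to each patient's outcome a lag that was complete before allocation. If that lag varies between patients, it can widen the interval for the arm difference. If the effect is expressed as a ratio, the shared extra days make it look smaller.

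What is at stake is the stated use of these estimates. They are to inform the design of future studies, and their intervals are already wide at the 99% level. An SD that includes the lag would also carry this site's enrolment delay into the next trial's sample size.

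**Working it through.** **The plan's own figure.** No precision or sample size is stated for time until recovery. The only figure is 154 per arm for the primary outcome, from 20% versus 10% progression, 80% power and a one-sided 0.05 error rate. The unpooled normal formula gives (1.645 + 0.842)² × (0.2×0.8 + 0.1×0.9) / 0.1² = 154.6, so the figure reproduces to within rounding. It is unaffected by this point and serves below only as the number per arm.

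**Inputs**
- From the documents: 154 per arm; clock starting at admission; no limit on the lag; no lag covariate.
- Assumed, because the documents give none of them: SD of R (days from randomisation to recovery) 4 to 10; SD of L (days from admission to randomisation) 0.5 to 3; correlation ρ between them −0.3 to +0.3. Every patient is treated as having a recovery time.

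**Formulas.** The admission-based outcome is R + L.
- Var(R+L) = SD_R² + SD_L² + 2ρ·SD_R·SD_L
- SE ratio = √[Var(R+L) / SD_R²]
- Effective n per arm = 154 / (SE ratio)²
- The admission clock loses precision only if ρ > −SD_L / (2·SD_R)

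**Results**

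| SD_R | SD_L | ρ | SE ratio | Effective n per arm |
|---|---|---|---|---|
| 10 | 0.5 | 0 | √(100.25/100) = 1.001 | 154 |
| 6 | 1 | 0 | √(37/36) = 1.014 | 150 |
| 6 | 2 | 0 | √(40/36) = 1.054 | 139 |
| 4 | 3 | 0 | √(25/16) = 1.250 | 99 |
| 6 | 2 | +0.3 | √(47.2/36) = 1.145 | 117 |
| 6 | 2 | −0.3 | √(32.8/36) = 0.955 | 169 |

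For SDs of 6 and 2 the break-even correlation is −2/(2×6) = −0.167. Below it the unadjusted admission clock is the more precise of the two.

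**Effect of adjusting for the lag.** In a linear model that includes L as a covariate, the treatment coefficient is the same from either origin, because the two outcomes differ by L itself. Its variance is proportional to (1 − ρ²)·SD_R², which is no larger than from either unadjusted clock. At ρ = −0.3 the relative SE is √0.91 = 0.954, against 0.955 for the unadjusted admission clock. So the apparent advantage of the admission clock disappears once the lag is a covariate.

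**Bias.** In a simulation (4,000 runs, 154 per arm, control recovery mean 8 days and SD 6, true difference −1 day, independent lag), the mean estimate was −0.98 to −0.99 from both origins.

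| Lag variance | SE from randomisation | SE from admission | SE from admission, lag adjusted |
|---|---|---|---|
| 1 | 0.667 | 0.676 | 0.667 |
| 3 | 0.680 | 0.707 | 0.680 |
| 6 | 0.674 | 0.731 | 0.677 |

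**Ratio scale.** Suppose recovery takes 7 versus 8 days from randomisation, a ratio of 7/8 = 0.875. With an assumed mean lag of 2 days, the admission clock gives 9/10 = 0.900. The difference of 1 day is unchanged. This matters only if a log link is used. The plan names distributions but no link, and it speaks of a difference in means.

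**The case against.** The strongest reply is that the effect may be small or absent. None of the SDs comes from the documents. If patients randomised later in their stay are closer to discharge, the correlation is negative and the admission clock can be the more precise one. That stands, so the loss must be stated as conditional. The remark about "a patient who is starting on study who has been on opioid based sedation for 3 days or more" is only weak evidence of late randomisation. Randomised patients must be on at most 6 L by nasal cannula, so sedated starters are more likely to be in the open-label group.

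A second reply is that admission has a use. Section 3.2 Statistical Analysis plans a comparison with matched chart patients outside the trial, who have no randomisation date. Admission is an origin that both groups share. The plan does not give this as its reason, but the choice cannot be called purposeless. Keeping an admission-based duration alongside preserves that use.

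Stronger readings that a reader might infer are not supported:
- **That the arm comparison is biased.** Randomisation balances the lag in expectation. A chance imbalance is part of the variance already counted.
- **That a percentage rise in variance loses the same percentage of the sample.** Effective n is divided by the inflation factor, so a 100% rise would lose 50%.
- **That a new origin would stop item 11 overlapping with length of stay.** Counted from the same origin, the two still differ only by the gap between being stable for discharge and leaving.
- **That non-randomised patients need their own origin for this purpose.** They are outside the full analysis set and do not enter the arm comparison.

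**Conclusion.** The point holds as a minor improvement. Item 11 counts days that treatment cannot affect, and the plan neither limits the lag nor adjusts for it. With uncorrelated lag and recovery time, and SDs in the assumed ranges, the cost is a standard error 0.1% to 25% larger. The middle case is 5.4%, or about 139 effective patients per arm instead of 154. The cost grows under positive correlation; at SDs of 6 and 2 it vanishes at a correlation of −0.167 and reverses below that. On a ratio scale there is dilution whenever the mean lag is above zero and the arms differ.

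The size cannot be fixed from the documents. The outcome is secondary and untested, and the primary analysis and its sample size are unaffected.

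**What to change.** For the two-arm comparison:

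1. Reword item 11 so that its clock starts at the date and time of randomisation, leaving its end event as it is. Do the same for length of stay when it is compared between arms.
2. Include days from admission to randomisation as a covariate in the models for both durations, and name time until recovery among the modelled durations.
3. Report that lag by arm as a baseline descriptor.
4. Keep the admission-based duration as a descriptive measure and for the matched chart comparison.

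The cost is a few lines of text. No new data should be needed: item 11 already requires the admission date, and section 3.1 already schedules laboratory tests by days since randomisation.
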